4.1.18 Pharmacodynamics

Blood samples will be used for PD testing (eg, Btk occupancy and B-cell activation). Refer to the laboratory binder for instructions on collecting and processing these samples. Testing will be done by the sponsor.

4.1.19 Pharmacokinetics

Refer to the laboratory manual for instructions on collecting and processing these samples. Testing will be performed at a central clinical laboratory. Leftover plasma samples may be used for exploratory *acalabrutinib* metabolite analyses. The predose sample can be taken up to 1 hour before dosing.

Table 4-1. Pharmacokinetic Sample Schedule

| Cycle | Day | HOURS POSTDOSE | | | | | | |
|-------|------------------|--|-----------------|---------------|---------------|----------------|----------------|---------------------------------|
| | | Predose | 0.5 (±5 min) | 1 (±5 min) | 2 (±5 min) | 4 (±10 min) | 6 (±10 min) | 24 (±30 min) |
| 1 | 1 | X | X | X | X | X | X | X*before Day 2 first dose |
| | 8 | X | X | X | X | X | X | |
| | 15, 22, 28 | Predose and 1 h (±5 min) postdose and 5 to 15 min before electrocar diogram (ECG) | | | | | | |

Note: All timepoints are relative to the morning dose.

4.1.20 Tumor Assessment

A pretreatment CT scan with contrast (unless contraindicated) is required of the chest, abdomen, and pelvis and any other disease sites (eg, neck) within 30 days before the first dose of study drug. A pretreatment positron-emission tomography (PET)/CT scan within 90 days before the first dose is also required. Information on extranodal involvement will also be recorded.

During treatment, CT scans with contrast (unless contraindicated) of the chest, abdomen, and pelvis and any other disease sites (eg, neck) will be done for tumor assessments at the end of Cycle 2 (± 7 days), Cycle 4 (± 7 days), and Cycle 6 (± 7 days); and then every 3 cycles (12 weeks, ± 7 days) thereafter or more frequently at investigator discretion. On-study tumor assessments will also be done by physical exam and laboratory results. Bone marrow and PET/CT are only required for confirmation of CR per clinical guidelines (see [Section 4.2](#)).

Note: For sites in Germany, radiologic tumor assessments will not include PET. Radiologic tumor assessments will be done at Screening and at the end of Cycle 2 (\pm 7 days) OR Cycle 4 (\pm 7 days) depending each on subjects' individual response; thereafter they will be done at investigator discretion. On-study tumor assessments will also be done by physical exam and laboratory results.

De-identified copies of all radiology results maybe requested by the sponsor.

Subjects should have radiographic tumor measurements done at the participating study center or an acceptable alternate imaging facility using an identical imaging protocol and similar equipment. The same imaging equipment should be used for all scans whenever possible. The same radiologist should be assigned to read all the scans for a given subject throughout the study.

In the event disease progression is suspected due to physical examination or laboratory test, a CT and PET/CT scan must be performed to confirm disease progression. There must be radiographically measurable disease at screening (\geq 1 lymph node $>$ 2.0 cm in the longest diameter). If the sole lesion lies within the field of prior radiotherapy, there must be evidence of disease progression in that lesion.

Up to 6 measurable lymph nodes (only target lesions $>$ 1.5 cm in the longest diameter may be assessed), clearly measurable in 2 perpendicular dimensions, will be followed as target lesions for each subject. Measurable sites of disease should be chosen such that they are representative of the subject's disease. In addition, selection of target lesions should be from as disparate regions of the body as possible when these areas are significantly involved. If additional lesions are present but are not included in the target lesion assessment, they can be added as non-target lesions followed throughout the study. The cranial-caudal measurement of the spleen and longest diameter of the liver will be assessed at screening and all subsequent response evaluations.

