3.4 SELECTION OF STUDY POPULATION

3.4.1 Inclusion Criteria

Eligible subjects will be considered for inclusion in this study if they meet **all** of the following criteria:

1. Men and women ≥ 18 years of age.
2. Eastern Cooperative Oncology Group (ECOG) performance status of ≤ 2 .
3. Pathologically confirmed de novo ABC DLBCL, and subjects **must have** available archival tissue for central pathology review to be eligible.
4. Relapsed or refractory disease, defined as either: 1) recurrence of disease after a CR, or 2) PR, SD, or progressive disease at completion of the treatment regimen preceding entry to the study (residual disease):
 - Subjects must have previously received a standard anthracycline and rituximab-based first-treatment regimen (eg, R-CHOP).
 - Subjects with suspected residual disease after the treatment regimen directly preceding study enrollment must have biopsy demonstration of residual DLBCL.
 - Subjects who have not received HDT/ASCT must be ineligible for HDT/ASCT as defined by meeting any of the following criteria:
 - Age ≥ 70 years
 - Diffuse lung capacity for carbon monoxide (DLCO) $< 50\%$ by PFT
 - Left ventricular ejection fraction (LVEF) $< 50\%$ by ECHO
 - Other organ dysfunction or comorbidities precluding the use of HDT/ASCT on the basis of unacceptable risk of treatment-related morbidity
 - Subject refusal of HDT/ASCT
 - Subjects who are intolerant to anthracycline-based first-line therapy and meet all other eligibility criteria including recurrent or refractory disease are also eligible.
5. Presence of radiographically measurable lymphadenopathy or extranodal lymphoid malignancy (defined as the presence of ≥ 1 lesion that measures ≥ 2.0 cm in the longest dimension and ≥ 1.0 cm in the longest perpendicular dimension as assessed by CT scan).
6. Agreement to use acceptable forms of contraception during the study and for 30 days after the last dose of study drug if sexually active and able to bear or beget children.

7. Agreement to refrain from sperm donation during the study and for 30 days after the last dose of study drug.
8. Willing and able to participate in all required evaluations and procedures in this study protocol including swallowing capsules without difficulty.
9. Ability to understand the purpose and risks of the study and provide signed and dated informed consent and authorization to use protected health information (in accordance with national and local patient privacy regulations).

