4.2 INVESTIGATOR'S ASSESSMENT OF RESPONSE TO TREATMENT

The investigator must rate the response of the subject's response to treatment consistent with clinical guidelines ([Cheson 2014](#)) as listed in [Table 4-2](#).

Table 4-2. Response Assessment Criteria for DLBCL (Cheson 2014)

| Response and Site | PET-CT-Based Response | CT-Based Response |
|---------------------------------------|--|--|
| Complete | Complete metabolic response | Complete radiologic response (all of the following) |
| Lymph nodes and extra lymphatic sites | Score 1, 2, or 3* with or without a residual mass on 5PS† It is recognized that in Waldeyer's ring or extranodal sites with high physiologic uptake or with activation within spleen or marrow (eg, with chemotherapy or myeloid colony-stimulating factors), uptake may be greater than normal mediastinum and/or liver. In this circumstance, complete metabolic response may be inferred if uptake at sites of initial involvement is no greater than surrounding normal tissue even if the tissue has high physiologic uptake | Target nodes/nodal masses must regress to ≤1.5 cm in LDi No extralymphatic sites of disease |
| Nonmeasured lesion | Not applicable | Absent |
| Organ enlargement | Not applicable | Regress to normal |
| New lesions | None | None |
| Bone marrow | No evidence of FDG-avid disease in the marrow | Normal by morphology; if indeterminate, IHC negative |
| Partial | Partial metabolic response | Partial remission (all of the following) |
| Lymph nodes and extra lymphatic sites | Score 4 or 5† with reduced uptake compared with baseline and residual mass(es) of any size At interim, these findings suggest responding disease At end of treatment, these findings indicate residual disease | ≥ 50% decrease in SPD of up to 6 target measurable nodes and extranodal sites When a lesion is too small to measure on CT, assign 5 mm × 5 mm as the default value When no longer visible, 0 × 0 mm For a node > 5 mm × 5 mm, but smaller than the normal, use actual measurement for calculation |
| Nonmeasured lesions | Not applicable | Absent/normal, regressed, but no increase |
| Organ enlargement | Not applicable | Spleen must have regressed by > 50% in length beyond normal |
| New lesions | None | None |

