consider a score of 3 as inadequate response (to avoid undertreatment). Measured dominant lesions: Up to six of the largest dominant nodes, nodal masses, and extranodal lesions selected to be clearly measurable in two diameters. Nodes should preferably be from disparate regions of the body and should include, where applicable, mediastinal and retroperitoneal areas. Non-nodal lesions include those in solid organs (eg, liver, spleen, kidneys, and lungs), GI involvement, cutaneous lesions, or those noted on palpation. Nonmeasured lesions: Any disease not selected as measured, dominant disease and truly assessable disease should be considered not measured. These sites include any nodes, nodal masses, and extranodal sites not selected as dominant or measurable or that do not meet the requirements for measurability but are still considered abnormal, as well as truly assessable disease, which is any site of suspected disease that would be difficult to follow quantitatively with measurement, including pleural effusions, ascites, bone lesions, leptomeningeal disease, abdominal masses, and other lesions that cannot be confirmed and followed by imaging. In Waldeyer's ring or in extranodal sites (eg, GI tract, liver, bone marrow), FDG uptake may be greater than in the mediastinum with complete metabolic response, but should be no higher than surrounding normal physiologic uptake (eg, with marrow activation as a result of chemotherapy or myeloid growth factors).

[†] PET 5PS: 1, no uptake above background; 2, Uptake \leq mediastinum; 3, uptake $>$ mediastinum but \leq liver; 4, uptake moderately $>$ liver; 5, uptake markedly higher than liver and/or new lesions; X, new areas of uptake unlikely to be related to lymphoma.

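### Section 4.1.20 limits measurable disease and target lesions to lymph nodes, contradicting inclusion criterion 5 and the Table 4-2 response rule, so eligibility and CT-based partial response can differ by site

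*Protocol*

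**What the plan says.** Three parts of the protocol say which disease must be present and which lesions are measured.

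- **Eligibility (Section 3.4.1, criterion 5).** The requirement is "Presence of radiographically measurable lymphadenopathy or extranodal lymphoid malignancy", met by one lesion of at least 2.0 cm in its longest dimension and at least 1.0 cm perpendicular to it on CT. Extranodal-only disease qualifies.
- **Tumor assessment (Section 4.1.20).** "There must be radiographically measurable disease at screening", which the section specifies as one or more lymph nodes longer than 2.0 cm. For follow-up it names "Up to 6 measurable lymph nodes", longer than 1.5 cm and clearly measurable in two perpendicular dimensions, as the target lesions. On everything else it says: "If additional lesions are present but are not included in the target lesion assessment, they can be added as non-target lesions". At baseline, "Information on extranodal involvement will also be recorded", with no rule for measuring it.
- **Response rating (Section 4.2, Table 4-2).** "The investigator must rate the response of the subject's response to treatment consistent with clinical guidelines", as set out in Table 4-2. CT-based partial response there is a fall of at least 50%, described as a "decrease in SPD of up to 6 target measurable nodes and extranodal sites". Stable disease uses the same set of lesions. The footnote defines the measured lesions as "Up to six of the largest dominant nodes, nodal masses, and extranodal lesions selected to be clearly measurable in two diameters".

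Section 5.1.1 gives response assessment to the investigators. Section 5.5.4 defines overall response rate (ORR) as the proportion with complete or partial response and starts duration of response (DOR) at the first such response.

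**The concern.** Target lesions are chosen once, at baseline, and Section 4.1.20 is where a site looks to choose them. If it is followed as worded, the SPD is a nodal quantity. Table 4-2, which turns the SPD into a response category, assumes one that includes extranodal lesions. The two sections can therefore give the same subject different CT-based categories.

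The screening sentence raises a separate problem: a subject can satisfy criterion 5 and fail Section 4.1.20. Whether that subject is enrolled depends on which section the site applies.

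At stake are who enters the trial, which partial responses count toward ORR, and when DOR starts. With investigator assessment at about 9 sites in up to 4 countries and no central response read described, nothing in the protocol would bring divergent site practice back into line.

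**Working it through.** There is no stated figure to reproduce; the check is a comparison of the text followed by short arithmetic.

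**1. Definitions side by side**

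| | Criterion 5 | Section 4.1.20 | Table 4-2 and footnote |
|---|---|---|---|
| Site of disease | Nodal or extranodal | Lymph node | Nodes, nodal masses, extranodal lesions |
| Longest diameter for entry | At least 2.0 cm | More than 2.0 cm | Not an entry rule |
| Short diameter for entry | At least 1.0 cm | No numeric minimum | Not an entry rule |
| Lesions in the SPD | Not stated | Up to 6 lymph nodes | Up to 6 nodes and extranodal sites |

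The entry rules differ in both directions. A node of exactly 2.0 by 1.0 cm meets criterion 5 but not 4.1.20. A node longer than 2.0 cm with a short diameter under 1.0 cm meets the 4.1.20 size limit but not criterion 5.

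**2. What each combination of readings does**

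| Entry rule applied | Target rule applied | Extranodal-only subject | Mixed-disease subject |
|---|---|---|---|
| Criterion 5 | Table 4-2 | Enrolled; SPD available | All measured lesions in SPD |
| Criterion 5 | 4.1.20 | Enrolled; no target lesion, no SPD | Nodal SPD only |
| 4.1.20 | 4.1.20 | Not enrolled | Nodal SPD only |
| 4.1.20 | Table 4-2 | Not enrolled | All measured lesions in SPD |

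Only the second row leaves an enrolled subject without an SPD. The second and third rows give a mixed-disease subject an SPD that differs from the Table 4-2 definition.

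**3. Mixed disease**

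Let s be the extranodal share of the baseline SPD over all measured lesions, a the fractional fall in the nodal part, and b the fractional fall in the extranodal part.

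- Fall under 4.1.20 = a.
- Fall under Table 4-2 = (1 − s)a + sb.

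Partial response needs 0.50 or more. As a non-target lesion, an extranodal mass meets the Table 4-2 partial-response row for nonmeasured lesions by regressing to any degree, so b may be close to 0. The Table 4-2 fall is then about (1 − s)a. If s exceeds 0.5, even complete disappearance of the nodes (a = 1) gives 1 − s < 0.50, which is short of partial response. Under 4.1.20 the same subject reaches it once a is 0.50.

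**4. Size**

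- One subject in 20: 1/20 = 5 percentage points of ORR.
- Extranodal-only subjects, illustration only. The number k is not in the protocol and is assumed to be 1, 2 or 4. The 24% partial response rate is the interim ibrutinib figure for ABC DLBCL cited in Section 1.2, so it belongs to another drug. Expected partial responses without a CT-based score = 0.24k: 0.24, 0.48 and 0.96. Divided by 20, that is 1.2, 2.4 and 4.8 points of ORR. These are upper bounds for the assumed k, because they place every such subject in the second row of step 2 with no PET-based response.
- Mixed disease: the protocol gives nothing from which to estimate how many subjects would be reclassified.

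**The case against.** The strongest reply is that the response rule is printed correctly and is mandatory. Section 4.2 obliges the investigator to rate by Table 4-2, which includes extranodal lesions in the SPD and in the measured set. A reader might infer from 4.1.20 that partial response cannot be scored in extranodal-only disease and that bulky extranodal disease goes unmeasured. The documents do not support either inference:

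- A site using Table 4-2 measures those lesions. The table also has a PET-based partial response that needs no SPD.
- If 4.1.20 is applied literally throughout, an extranodal-only subject is not enrolled, so no response is lost. The loss requires criterion 5 to govern entry and 4.1.20 then to govern scoring.
- Section 4.1.20 calls for CT of all disease sites, asks for targets representative of the disease, and allows other lesions to be followed as non-target. Table 4-2 uses those lesions for complete response, partial response and progression.
- Progression can be declared on any individual lesion, on nonmeasured disease or on a new extranodal site. The effect on progression-free survival is therefore not established.

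These points limit the consequence but leave the contradiction. Table 4-2 cannot supply a baseline SPD that a site following 4.1.20 never recorded. The PET route is narrow: on-treatment PET/CT is required only to confirm complete response or suspected progression, and sites in Germany do not use PET. The request for representative sites does not lift the lymph-node wording in the sentence before it.

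It is also fair to say that safety is the primary objective, that response is secondary, and that no hypothesis test is planned. That bears on severity.

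**Conclusion.** The inconsistency is real and is in the current text. Section 4.1.20 conflicts with criterion 5 on who has measurable disease and with Table 4-2 on which lesions form the SPD. Eligibility, CT-based partial response, ORR and the start of DOR can therefore vary with the section a site follows.

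The supportable size is 5 percentage points of ORR per affected subject, assuming a denominator of 20. How many subjects are affected is unknown, and the range in the working rests on assumed counts and another drug's response rate. It would go too far to say that the protocol as a whole makes partial response unscorable in extranodal disease, because the mandatory table provides for it.

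Severity is moderate: an internal inconsistency affecting an untested secondary endpoint, worth correcting but not a must-fix.

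**What to change.** Two sentences in Section 4.1.20 need to change.

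1. Reword the target-lesion sentence to match the Table 4-2 footnote, so that nodes, nodal masses and extranodal lesions measurable in two diameters can all be among the six.
2. Reconcile the measurable-disease sentence with criterion 5, so that one definition and one size threshold apply at screening. The sponsor should settle which limits are intended and state them once, with a cross-reference from the other place.

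Any imaging or eCRF completion guidance should carry the same wording. For subjects already enrolled, the sponsor could check from existing scans whether measurable extranodal lesions were left out of the baseline targets. The cost is an edit to the text and guidance; the scans and procedures stay the same.

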4.1.21 Routine Clinical Assessments

Routine clinical assessments include physical exams, recording of symptoms, and hematologic evaluations to evaluate for both AEs and assessment of disease progression at times when the CT and/or PET/CT scan is not obtained. The investigator should report any suspected disease progression to the sponsor or designee via the electronic data capturing (EDC) system within 24 hours of discovery.

4.1.22 Study Drug Accountability

See [Section 7.7](#).

4.2 INVESTIGATOR'S ASSESSMENT OF RESPONSE TO TREATMENT

The investigator must rate the response of the subject's response to treatment consistent with clinical guidelines ([Cheson 2014](#)) as listed in [Table 4-2](#).

Table 4-2. Response Assessment Criteria for DLBCL (Cheson 2014)

| Response and Site | PET-CT-Based Response | CT-Based Response |
|---------------------------------------|--|--|
| Complete | Complete metabolic response | Complete radiologic response (all of the following) |
| Lymph nodes and extra lymphatic sites | Score 1, 2, or 3* with or without a residual mass on 5PS† It is recognized that in Waldeyer's ring or extranodal sites with high physiologic uptake or with activation within spleen or marrow (eg, with chemotherapy or myeloid colony-stimulating factors), uptake may be greater than normal mediastinum and/or liver. In this circumstance, complete metabolic response may be inferred if uptake at sites of initial involvement is no greater than surrounding normal tissue even if the tissue has high physiologic uptake | Target nodes/nodal masses must regress to ≤1.5 cm in LDi No extralymphatic sites of disease |
| Nonmeasured lesion | Not applicable | Absent |
| Organ enlargement | Not applicable | Regress to normal |
| New lesions | None | None |
| Bone marrow | No evidence of FDG-avid disease in the marrow | Normal by morphology; if indeterminate, IHC negative |
| Partial | Partial metabolic response | Partial remission (all of the following) |
| Lymph nodes and extra lymphatic sites | Score 4 or 5† with reduced uptake compared with baseline and residual mass(es) of any size At interim, these findings suggest responding disease At end of treatment, these findings indicate residual disease | ≥ 50% decrease in SPD of up to 6 target measurable nodes and extranodal sites When a lesion is too small to measure on CT, assign 5 mm × 5 mm as the default value When no longer visible, 0 × 0 mm For a node > 5 mm × 5 mm, but smaller than the normal, use actual measurement for calculation |
| Nonmeasured lesions | Not applicable | Absent/normal, regressed, but no increase |
| Organ enlargement | Not applicable | Spleen must have regressed by > 50% in length beyond normal |
| New lesions | None | None |
| Bone marrow | Residual uptake higher than uptake in normal marrow but reduced compared with baseline (diffuse uptake compatible with reactive changes from chemotherapy allowed). If there are persistent focal changes in the marrow in the context of a nodal response, consideration should be given to further evaluation with MRI or biopsy or an interval scan | Not applicable |

Footnotes appear after the last page of the table.

Table 4-2. Response Assessment Criteria for DLBCL (Cheson 2014) (continued)

| Response and Site | PET-CT-Based Response | CT-Based Response |
|---|--|--|
| No response or stable disease | No metabolic response | Stable disease |
| Target nodes/nodal masses, extranodal lesions | Score 4 or 5 with no significant change in FDG uptake from baseline at interim or end of treatment | < 50% decrease from baseline in SPD of up to 6 dominant, measurable nodes and extranodal sites; no criteria for progressive disease are met |
| Nonmeasured lesions | Not applicable | No increase consistent with progression |
| Organ enlargement | Not applicable | No increase consistent with progression |
| New lesions | None | None |
| Bone marrow | No change from baseline | Not applicable |
| Progressive disease | Progressive metabolic disease | Progressive disease requires at least 1 of the following |
| Individual target nodes/nodal masses | Score 4 or 5 with increase in intensity of uptake from baseline and/or | PPD progression: |
| Extranodal lesions | New FDG-avid foci consistent with lymphoma at interim or end-of-treatment assessment | An individual node/lesion must be abnormal with: LDi > 1.5 cm and Increase by ≥ 50% from PPD nadir and An increase in LDi or SDi from nadir 0.5 cm for lesions ≤ 2cm 1.0 cm for lesions > 2 cm In the setting of splenomegaly, the splenic length must increase by > 50% of the extent of its prior increase beyond baseline (eg, a 15-cm spleen must increase to >16 cm). If no prior splenomegaly, must increase by at least 2 cm from baseline New or recurrent splenomegaly |
| Nonmeasured lesions | None | New or clear progression of preexisting nonmeasured lesions |
| New lesions | New FDG-avid foci consistent with lymphoma rather than another etiology (eg, infection, inflammation). If uncertain regarding etiology of new lesions, biopsy or interval scan may be considered | Regrowth of previously resolved lesions A new node > 1.5 cm in any axis A new extranodal site >1.0 cm in any axis; if < 1.0 cm in any axis, its presence must be unequivocal and must be attributable to lymphoma Assessable disease of any size unequivocally attributable to lymphoma |
| Bone marrow | New or recurrent FDG-avid foci | New or recurrent involvement |

Abbreviations: 5PS, 5-point scale; CT, computed tomography; FDG, fluorodeoxyglucose; IHC, immunohistochemistry; LDi, longest transverse diameter of a lesion; MRI, magnetic resonance imaging; PET positron emission tomography; PPD, cross product of the LDi and perpendicular diameter; SDi, shortest axis perpendicular to the LDi; SPD, sum of the product of the perpendicular diameters for multiple lesions.

*A score of 3 in many patients indicates a good prognosis with standard treatment, especially if at the time of an interim scan. However, in trials involving PET where de-escalation is investigated, it may be preferable to

consider a score of 3 as inadequate response (to avoid undertreatment). Measured dominant lesions: Up to six of the largest dominant nodes, nodal masses, and extranodal lesions selected to be clearly measurable in two diameters. Nodes should preferably be from disparate regions of the body and should include, where applicable, mediastinal and retroperitoneal areas. Non-nodal lesions include those in solid organs (eg, liver, spleen, kidneys, and lungs), GI involvement, cutaneous lesions, or those noted on palpation. Nonmeasured lesions: Any disease not selected as measured, dominant disease and truly assessable disease should be considered not measured. These sites include any nodes, nodal masses, and extranodal sites not selected as dominant or measurable or that do not meet the requirements for measurability but are still considered abnormal, as well as truly assessable disease, which is any site of suspected disease that would be difficult to follow quantitatively with measurement, including pleural effusions, ascites, bone lesions, leptomeningeal disease, abdominal masses, and other lesions that cannot be confirmed and followed by imaging. In Waldeyer's ring or in extranodal sites (eg, GI tract, liver, bone marrow), FDG uptake may be greater than in the mediastinum with complete metabolic response, but should be no higher than surrounding normal physiologic uptake (eg, with marrow activation as a result of chemotherapy or myeloid growth factors).

[†] PET 5PS: 1, no uptake above background; 2, Uptake \leq mediastinum; 3, uptake $>$ mediastinum but \leq liver; 4, uptake moderately $>$ liver; 5, uptake markedly higher than liver and/or new lesions; X, new areas of uptake unlikely to be related to lymphoma.

